- To assess the pharmacokinetics (PK), pharmacodynamics (PD), and PK/PD associations of AMG 714.

The **exploratory endpoints** of the study are:

- PK;
- PD;
- Exposure/response (PK/PD).

PK data will be tabulated by timepoint. Exploratory PD endpoints are aberrant and abnormal IELs by flow cytometry, immunochemistry and T cell receptor (TcR) clonality analyses, Physician Global Assessment of Disease (PGA) and Patient Global Assessment of Disease (PtGA), Quality of Life Assessments (i.e. SF-12 v. 2 and EQ-5D), biomarkers of disease activity (i.e., serum IL-15, CD122 and granzyme B) and Celiac Disease Patient Reported Outcome (CeD PRO). The exploratory PD endpoints will be evaluated by investigating the change from baseline and weekly scores, if applicable, of AMG 714 dose arm and placebo arm.

3 Study type and design

CELIM-RCD-002 is designed to be a Phase 2a randomized, double-blind, placebo-controlled, parallel-group study to evaluate the efficacy and safety of AMG 714 for the treatment of adult patients with RCD-II, an in situ small bowel T cell lymphoma.

After signing informed consent, subjects will be screened for the study. All subjects who meet the study entry criteria will be randomized at a 2:1 ratio to receive either 8 mg/kg AMG 714 or placebo for a total of 7 times over 10 weeks, with evaluation of the primary endpoint at Visit 8 (Week 12/Day 84).

AMG 714 (N=16) or placebo (N=8) will be administered at the clinical site in a double-blind fashion via intravenous (IV) infusion of approximately 120 minutes (2 hours) duration.

Subjects will remain confined to the study site for a minimum of 1 hour after the administration of study medication. During this time the investigator and study site staff will assess the subject for adverse events (AEs). As per [Appendix 1](#), PK samples are to be collected prior to the infusion and 1 hour after the infusion, at the end of this observation period. The beginning and end of each infusion, as well as the PK sample collection times, will be recorded.

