where $\mu_{AMG\ 714}$ and $\mu_{placebo}$ denote the mean baseline to Week 12 relative (%) change in % aberrant IELs vs total IELs as assessed by flow-cytometry in the AMG 714 and placebo arm, respectively. The hypotheses will be tested using a two-sided, 0.10 level of significance.

7 Estimation of sample size

The CELIM-RCD-002 study is an exploratory proof-of-concept (POC) study of an experimental medication, AMG 714, in RCD-II patients. While it will be the first such study sponsored by a pharmaceutical company, the straightforward design is based on several academic studies (Goerres *et al*, 2003; Brar *et al*, 2007; Tack *et al*, 2011a, 2011b) as well as on the nonclinical proof-of-principle signal obtained with AMG 714 in intestinal explants from patients with RCD-II (Malamut *et al*, 2010).

The sample size is based on the size of previous academic studies. Published prospective academic studies have ranged from 13 to 18 subjects total (Tack *et al*, 2011a, 2011b) and CELIM-RCD-002 will be the largest prospective trial ever conducted in RCD-II, a very rare malignant disease.

The sample size of 24 subjects (16 subjects in AMG 714 arm and 8 subjects in placebo arm) has been calculated to achieve at least ~ 80% power to detect a 20 percentage point difference in the primary endpoint, the difference in the baseline-to-Week 12 reduction of % aberrant IELs vs total IELs between the AMG 714 arm and placebo arm.

This sample size calculation was based on the following assumptions:

- Two-sided type one error rate $\alpha = 0.1$.
- Power $1-\beta = 0.8$.
- Analysis method: one-way analysis of variance (ANOVA) by SAS[®] (proc power).
- 2:1 allocation ratio between the AMG 714 and placebo arms.
- Common SD = 17.4 for the baseline to Week 12 reduction in % aberrant IELs as assessed by flow-cytometry.

- Mean change of 20 percentage points and 0 percentage points in the baseline to Week 12 reduction in % aberrant IELs in the AMG 714 and placebo arms, respectively.

The standard deviation used for the sample size calculation is computed from the % aberrant IELs (obtained by flow-cytometry) data from 13 subjects treated with cladribine (subset of the subjects reported in Tack et al, 2011).

8 Statistical methods

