8.2 General statistical considerations

Descriptive statistics (e.g. mean, median, standard deviation (SD), minimum (MIN), maximum (MAX), and number of subjects with an observation (N) or missing observation (NMISS)) are used for summarizing continuous variables. Additional statistics will be provided for PK-related data, including the geometric mean, SD of log-transformed data, geometric CV% and geometric N (i.e. number of subjects with an observation that are included in the natural logarithmic transformation).

Frequencies and percentages are used for summarizing categorical variables.

All summary statistics will be presented by treatment arm and if repeated measures, then by visit/collection time point.

All listings will be created using ITT population. The PP and ITT flags for each subject will be included in all listings.

All tests will be two-sided, if not stated differently. P-values smaller than 0.1 (for primary hypothesis) or 0.05 (all other hypotheses) will be considered statistically significant. In addition to the inferential statistics, 90% or 95% confidence intervals will be constructed. For the primary endpoint a 90% confidence interval of the treatment difference will be

constructed. Ninety-five percent (95%) confidence intervals will be constructed for the individual treatment point estimates.

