$$Y_{ijk} = \mu + \alpha_j + \gamma_k + \lambda_{jk} + \beta \cdot \text{baseline GSRs}_{ij} + \eta_i + \varepsilon_{ijk},$$

where

Y_{ijk} is the absolute change from baseline in total GSRs score for subject i ($i = 1, \dots, n_j$) from treatment group j ($j = 1, 2$) at week k ($k = 1, 2, \dots, 16$),

μ is the overall mean,

The baseline and post-baseline total GSRS scores along with the change from baseline values will also be described by summary statistics and tabulated by treatment group. In addition to that, the baseline and post-baseline scores of all 15 questions and for the mean total scores of five dimensions of gastrointestinal syndromes (diarrhoea (questions 11, 12 and 14), indigestion (questions 6-9), constipation (questions 10, 13 and 15), abdominal pain (questions 1, 4 and 5) and reflux (questions 2 and 3)) along with the change from baseline values will be described by summary statistics and tabulated by treatment group. Both the scores of individual questions and the total GSRS scores will also be listed. Mean total GSRS scores as well as the scores of the individual questions, will also be presented graphically by time point and treatment group.

ITT population will be used for the analysis as long as there is a baseline and post-treatment measure (i.e., not lost to follow-up).

Change from baseline in clinical symptoms: the celiac disease GSRS (CeD-GSRS)

The CeD-GSRS is formed by the subset of questions from GSRS questionnaire (questions 1, 4-9, 11, 12 and 14).

The total CeD-GSRS score is calculated as the mean of scores of all 10 questions in CeD-GSRS questionnaire, with the scores of the questions between 1 (No discomfort at all) and 7 (Very severe discomfort). Therefore, the smaller the total CeD-GSRS score, the milder the symptoms of the subject.

The change from baseline in CeD-GSRS will be analysed using a linear mixed effects repeated measures model (MMRM) with the baseline value, treatment group, time point and a time point-by-treatment group interaction term as fixed effects with an underlying correlation structure between the time points that results in the best fit for the model. Subject will be included as a random effect. The following model will be fitted:

$$Y_{ijk} = \mu + \alpha_j + \gamma_k + \lambda_{jk} + \beta \cdot \text{baseline CeD GSRS}_{ij} + \eta_i + \varepsilon_{ijk},$$

where

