The modelling results (parameter estimates, covariance parameter estimates, estimated treatment effect, marginal means estimates and results of the check of assumptions) will be tabulated and 95% confidence intervals added, where appropriate. If the parametric assumptions are not met, then in addition to the above-specified model, a generalized estimating equation (GEE) approach will be used as well.

The baseline and post-baseline total weekly CeD-GSRS scores along with the change from baseline values will also be described by summary statistics and tabulated by treatment group. The total weekly CeD-GSRS scores will also be listed. Mean total weekly CeD-GSRS will also be plotted by time point and treatment group.

ITT population will be used for the analysis.

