ods output CovParms=Cov_Par LSMeans=LS_est Estimates=Eff_est  
FitStatistics=Fit_Stat ParameterEstimates=Par_est  
Tests3=Type_3;  
  
run;
```

Due to the repeated structure of the data, the measurements within a subject will be correlated. Therefore, it is assumed that the overall covariance matrix of the response is block-diagonal (e.g. the observations between different subjects are not related, but the same correlation structure exists within subjects). In order to determine the covariance structure that best fits the data, the same model with different covariance structures is fitted. Initially, the models will be fitted assuming first-order autoregressive (AR(1)) variance-

covariance structure. Common within and between treatment variance components (compound symmetry (CS), and Toeplitz covariance structures) will be further explored to increase sensitivity of statistical tests. The best model will be chosen by comparing the Akaike Information Criterion (AIC) of the models with different covariance structures.

Note that the value of `type` will be changed according to which covariance structure is being fitted.

The modelling results (parameter estimates, covariance parameter estimates, estimated treatment effect, marginal means estimates and results of the check of assumptions) will be tabulated and 95% confidence intervals added, where appropriate. If the parametric assumptions are not met, then in addition to the above-specified model, a generalized estimating equation (GEE) approach will be used as well.

The baseline and post-baseline weekly total CeD PRO scores along with the change from baseline values will also be described by summary statistics and tabulated by treatment group. Change from baseline for the weekly CeD PRO scores of individual questions (calculated as the average score of a question within a week) will also be tabulated by week and treatment group and described by summary statistics. The scores of individual questions and the total daily CeD PRO scores will be listed, as well as the total and by question weekly CeD PRO scores. Mean curves of both the total weekly and daily CeD PRO scores as well as the individual questions will also be plotted by time point and treatment group.

A tabulation of the proportion of subjects with at least a 50% change from baseline for ≥ 6 weeks will be provided. This analysis will be done internally by Celimmune.

ITT population will be used for summarizing CeD PRO results.

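### The GEE added to the CeD-GSRS and CeD PRO models has no stated variance estimator, reference distribution or rank against the MMRM; with 16 and 8 subjects its usual uncorrected form rejects a true null about 8–10% of the time at nominal 5%

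*SAP*

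**What the plan says.** - **CeD-GSRS (SAP 8.6.2, secondary).** Change from baseline is analysed by an MMRM "with the baseline value, treatment group, time point and a time point-by-treatment group interaction term as fixed effects". SAS code is given, and the covariance structure is chosen by AIC. If the checks fail, then besides that model "a generalized estimating equation (GEE) approach will be used as well".
- **CeD PRO (SAP 8.7.6, exploratory).** After the daily and weekly models comes the same rule: "If the parametric assumptions are not met, then in addition to the above-specified model, a generalized estimating equation (GEE) approach will be used as well".
- **Significance (SAP 8.2).** "All tests will be two-sided, if not stated differently", and "P-values smaller than 0.1 (for primary hypothesis) or 0.05 (all other hypotheses) will be considered statistically significant". These two endpoints are therefore judged at 0.05, with 95% intervals.
- **Size (SAP 7).** "16 subjects in AMG 714 arm and 8 subjects in placebo arm".

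Each GEE rule is one sentence. Neither document gives the working correlation, the variance estimator, a small-sample correction or the reference distribution, or says whether the MMRM or the GEE prevails. SAP 8.6.1 also allows SAS code to be changed on statistical grounds without amending the SAP.

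**The concern.** A GEE's robust (sandwich) variance is justified when there are many independent subjects. Here there are 24, with 8 in one arm. Sixteen weekly scores per subject do not add independent units. At this size the uncorrected sandwich is too small on average and is itself noisy, so a normal reference makes the test liberal. The analysis meant to cover doubtful assumptions then brings an error rate of its own.

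The trigger is plausible. CeD-GSRS is a mean score bounded between 1 and 7. Protocol 9.1 (note to criterion 4) admits previously treated or steroid-treated subjects without current symptoms, so floor effects could occur. Since the SAP labels any non-primary p-value below 0.05 significant, a liberal GEE p-value for a symptom endpoint would carry that label beside an MMRM already in doubt.

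**Working it through.** **1. The plan's own figure.** The documents give no error rate for the GEE. The stated figure that can be reproduced is the sample size (SAP 7): difference 20, SD 17.4, two-sided alpha 0.10, power 0.80, allocation 2:1.

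- Placebo n = (1.645 + 0.842)² × 17.4² × (1 + 1/2) / 20² = 7.02, rounded up to 8; active 16; total 24.
- Power with 16 and 8: noncentrality 20 / (17.4 × √(1/16 + 1/8)) = 2.65. The noncentral t gives 82.3%; 14 and 7 subjects give 77.3%.

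So 16 and 8 is the planned number of independent units.

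**2. Size of the bias by hand.** Take one value per subject, equal variance σ² and no covariate. A subject's leverage h is 1/16 (active) or 1/8 (placebo), and the expected squared residual is σ²(1 − h).

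- True variance of the difference: σ²(1/16 + 1/8) = 0.1875σ².
- Expected uncorrected sandwich: σ²[(1/16)(15/16) + (1/8)(7/8)] = 0.1680σ², a ratio of 0.896.
- Standard error ratio: √0.896 = 0.946. The cut-off of 1.96 acts like 1.96 × 0.946 = 1.855, a two-sided error of about 6.4%.
- Kauermann-Carroll divides each squared residual by (1 − h), so its expectation is 0.1875σ², unbiased in this simple case.
- Mancl-DeRouen divides by (1 − h)², giving σ²[(1/16)(16/15) + (1/8)(8/7)] = 0.2095σ², a ratio of 1.117. This is why it is conservative.

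Bias alone takes 5% to about 6.4%. Noise in the variance estimate and the baseline covariate add the rest, which needs simulation.

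**3. Simulation under a true null.** Inputs from the SAP: 16 and 8 subjects; baseline, treatment, week and treatment-by-week terms; weekly scores (16 post-baseline weeks); two-sided 5%. Assumptions, because the documents give none: true correlation compound symmetric 0.5–0.6 or AR(1) 0.7–0.8; working correlation independence, exchangeable or AR(1); normal or skewed errors; complete data. Runs had 4,000 to 40,000 replicates, plus 400,000 for the equivalent subject-level regression. Monte Carlo standard error is about 0.45 points at 4,000 replicates.

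| Uncorrected sandwich, normal (z) reference | Rejection at nominal 5% |
|---|---|
| Average over weeks, 400,000 replicates | 9.2–9.3% |
| Average over weeks, 4,000 replicates | 8.5–8.9% |
| Week 12, 40,000 replicates | 8.6–9.0% |
| Week 12, 4,000 replicates | 8.2–8.6% |
| No baseline covariate | 8.3–8.4% |
| 15/7 or 14/7 subjects | 9.7–10.0% |
| Placebo SD 1.5 times active | 10.2% |
| Active SD 1.5 times placebo | 8.6% |

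| Other versions, 16 and 8 subjects, equal variances | Rejection at nominal 5% |
|---|---|
| Uncorrected sandwich, t reference | 6.6–7.7% |
| Kauermann-Carroll, t on 21 df | 5.1–5.7% |
| Mancl-DeRouen, t on 21 df | 3.6–4.4% |
| Mancl-DeRouen, z reference | 4.8–5.4% |

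Here 21 = 24 subjects − 3 between-subject parameters (intercept, treatment, baseline). The rates hardly move with the correlation structure or skewness. With 15/7 or 14/7 subjects and the baseline covariate, the uncorrected sandwich with a t reference gives 7.7–8.0%.

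**4. Limits of the check.** All corrected rates are for one-degree-of-freedom contrasts. The daily CeD PRO model and missing diary entries were not simulated. A joint 15-df Wald test of treatment-by-week with the uncorrected sandwich rejected about 93% of the time under the null; the SAP does not say that such a test would be taken from the GEE.

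**The case against.** The strongest reply is that the SAP never prescribes the uncorrected sandwich or a normal reference. That stands. A reader might infer that the plan specifies a test with twice its stated error rate, but the documents do not support this. The gap is an unspecified estimator, and the inflation follows only if the classical form is used. With a t reference it falls to about 7–8%.

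The second reply is that the GEE does not replace the MMRM. That also stands: both sections add it to the specified model, whose results are tabulated with 95% intervals. A reader might infer that a symptom benefit could be claimed from the GEE alone, but nothing in the SAP gives the GEE precedence. Nothing denies it either, and the 0.05 label in SAP 8.2 applies to any non-primary test, so a precedence rule is still needed.

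Third, the stakes are limited. The study is an exploratory proof of concept, CeD PRO is described in SAP 8.7.6 as not validated in RCD-II, and the Go/No-Go rule in Protocol 13.1 rests on the two Immunological Response calculations, neither analysed by GEE. This limits the weight of the point but does not answer it.

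Last, correction can overshoot: Mancl-DeRouen with a t reference falls below 5%. This is fair, and is a reason to consider Kauermann-Carroll.

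**Conclusion.** The point holds in conditional form. The SAP leaves the GEE's variance estimator, small-sample correction, reference distribution and rank against the MMRM open for CeD-GSRS and CeD PRO. If it is run with the usual uncorrected sandwich and a normal reference, the two-sided error rate at 16 and 8 subjects is about 8–10% instead of 5%, or 1.6 to 2 times nominal; with a t reference it is about 7–8%. The 95% intervals are too narrow to match.

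These rates assume complete weekly data and the mean model in the SAP. The correlation and error distributions are assumptions, but varying them changed little. The corrected rates assume equal variances in the arms; a more variable placebo arm would raise them somewhat.

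It would go too far to say that the trial's conclusion is at risk: the primary ANCOVA and the Go/No-Go rule do not use a GEE. The GSRS model text is incomplete in the copy read, so no claim is made about GSRS.

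**What to change.** In SAP 8.6.2 (CeD-GSRS) and 8.7.6 (CeD PRO), extend the GEE sentence to state:

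1. The covariance is a bias-corrected sandwich. Kauermann-Carroll is closest to nominal (about 5–6%); Mancl-DeRouen (about 4%) suits a preference for slight conservatism.
2. Tests and 95% intervals use a t reference on between-subject degrees of freedom (21 with all 24 subjects), not the number of weekly records.
3. The MMRM remains the main result and the GEE is a sensitivity analysis, whichever gives the smaller p-value.

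The cost is one or two sentences, a covariance option and a degrees-of-freedom setting. GEE intervals become wider. Using step 2 of the working and t = 2.080 on 21 df, the factor against the uncorrected normal interval is roughly (2.080 / 1.960) × √(0.1875 / 0.1680) = 1.12 for Kauermann-Carroll and (2.080 / 1.960) × √(0.2095 / 0.1680) = 1.19 for Mancl-DeRouen. No change to data collection, sample size or the primary analysis is needed.

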8.7 Exploratory analysis

The exploratory endpoints of the study are:

- Reduction in aberrant and abnormal IELs by flow cytometry, immunohistochemistry and TcR clonality analyses (including % of patients with normalization in IELs);
- PGA and PtGA;
- Quality of Life Assessments:
 - SF-12 v. 2;
 - EQ-5D;
- Biomarkers of disease activity;
- PK, and PK/PD correlations;
- CeD PRO;
- Assessment of the gluten-free diet (iVYLISA GIP stool test and dietician consultation).

8.7.1 Reduction in aberrant and abnormal IELs by flow cytometry, immunohistochemistry and T cell receptor (TcR) clonality analyses

Aberrant IELs were narrowly defined in [Section 2](#) for the purpose of primary and secondary endpoint analysis. In addition to these aberrant IELs, found by definition in the intestinal epithelium, cells with identical characteristics can be measured in the *lamina propria* of the mucosa (“aberrant IELs in the *lamina propria*”) and -should the aberrant IELs leave the gut mucosa to spread to other tissues- in peripheral blood also (“aberrant IELs in blood”). These cells will be assessed.

In addition to the frequency of aberrant IELs, multiple markers will be studied in IELs which may identify other abnormal IELs, defined as IELs with an inflammatory (e.g., Granzyme B-positive) or otherwise abnormal phenotype or a phenotypically normal population with abnormal prevalence in blood or biopsy tissue. These phenotypes and abnormalities may also be assessed in aberrant IELs.

IEL abnormalities may be detected by several methods, such as flow cytometry, immunohistochemistry, or with TcR clonality analyses (a method to detect abnormal and also aberrant IELs by quantifying the characteristic T cell Receptor, which is monoclonal in aberrant IELs).

While aberrant IELs are pre-defined in primary and secondary endpoints based on surface and intracellular CD3 expression by flow cytometry (and CD8 expression by IHC), at this time it is not possible to predict which other populations of IELs may be abnormal and may require analysis, which will be done ad-hoc in an exploratory fashion.

Percentages and counts of aberrant and abnormal IELs by flow cytometry, immunochemistry or TcR clonality, and changes from baseline will be presented using summary statistics by treatment group and visit. Specifically, the % of Granzyme B-positive aIELs and IELs, as well as the mean fluorescence intensity of the Granzyme B expression in those and other cell types, will be summarized and analysed by treatment group.

PP population will be used for summarizing these results.

These analyses will be done internally at Celimmune.

8.7.2 Physician Global Assessment of Disease (PGA) and Patient Global Assessment of Disease (PtGA)

The PGA is designed to be used by the Investigator or qualified designee to assess the subjects' disease activity at the time points specified in the study schedule of events (Appendix 1). An attempt should be made to use the same assessor at each specified time point. Part B of the PGA is designed to assess physician perception of change in disease activity. Part B should be completed as per the schedule of events (Appendix 1) beginning after Visit 1, Week 0/Day 0.

The PtGA is designed to be used by the subject to assess perception of disease activity at the time points listed in Appendix 1. Part B of the PtGA, is designed to assess subject perception of change in disease activity and should be completed as per the schedule of events (Appendix 1) beginning after Visit 1, Week 0/Day 0.

Both PGA and PtGA are filled in on paper.

PGA and PtGA will be tabulated by treatment group, visit and part (PGA/PtGA part A, PGA/PtGA part B). Change from baseline in PGA and PtGA part A will be presented by treatment group and visit. All PGA and PtGA results will also be listed. Mean PGA and PtGA results will also be plotted by visit and treatment group.

As an exploratory assessment, Week 12 PGA scores will be dichotomized for an outcome endpoint where scores ≤ 2 will be considered treatment success and scores > 2 will be considered treatment failure. Assessment of differences in treatment proportions will be conducted.

ITT population will be used for summarizing PGA and PtGA results.

